This study is an experimental study with a pre-post-test design. This design refers to a previous study by von Schwarz et al. which used stem cell injections in erectile dysfunction patients. This study was an experimental study with a pre-post-test research design with 12 subjects of severe ED non-responsive to sildenafil. The study involved men aged 40-65 years with severe erectile dysfunction unresponsive to sildenafil therapy, and samples were taken using a consecutive sampling technique.

The safety parameters measured included pain, hematoma, local bleeding, and infection. Efficacy parameters were measured through the IIEF-5 questionnaire, EHS, morning erection, SPL, FPL, penis circumference, and several ED evaluation examinations by PDCU. Color Doppler ultrasonography is an informative and minimally invasive tool useful in the diagnosis and evaluation of erectile dysfunction, especially in the evaluation of penile hemodynamics. Spectral Doppler analysis of the cavernosal arteries in the flaccid penis is a non-invasive method for assessing arterial disease and has been reported to have the best accuracy for predicting arterial insufficiency using a PSV cutoff value of 10cm/s in the cavernosal arteries.

Statistical Analysis Plan (SAP)

Analysis of the Safety and Efficacy of Administering Umbilical Cord Mesenchymal Stem Cell Secretome in Patients With Severe Erectile Dysfunction Non-responsive to Sildenafil

Date : 6 October 2025

1. Outcomes (sign, symptoms and questionnaire result)

One of the study aimed to measure the effect of umbilical cord mesenchymal stem cell secretome administration on outcomes such as pain, hematoma, local bleeding, infection, and changes in IIEF-5, EHS, and morning erections. The Wilcoxon analysis will be used to compare outcomes before and after intervention at various times

2. SPL, FPL and Penis Cicumference

One of the study aimed to measure the effect of umbilical cord mesenchymal stem cell secretome administration on SPL, FPL, and Penis Circumference. The Paired T test wil be used to compare outcomes before and after intervention at various times.

3. PSV and Diameter of cavernosum artery

The study subjects underwent PCDU examination while flaccid to assess both research parameters, namely Peak Systolic Velocity (PSV) and the diameter of the proximal side cavernosum artery lumen before and 1 month after the intracavernosal injection intervention. The difference in PSV of the right and left cavernosum arteries will be analyzed using the Paired T-test.

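### Hematoma, local bleeding and infection are analysed only by a before/after Wilcoxon test, which gives no complication rate and no upper bound on harm

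*SAP*

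**What the plan says.** The Protocol (Materials and Methods) names the safety endpoints, "The safety parameters measured included pain, hematoma, local bleeding, and infection", and gives no analysis for them. Section 1 of the SAP groups them as "outcomes such as pain, hematoma, local bleeding, infection, and changes in IIEF-5, EHS, and morning erections" and assigns one method to the whole group: "The Wilcoxon analysis will be used to compare outcomes before and after intervention at various times".

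Sections 2 and 3 of the SAP cover penile measurements and Doppler parameters with paired t-tests; no safety outcome appears there. Section 3 gives the route and one time point, "before and 1 month after the intracavernosal injection intervention".

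Neither document plans a count or proportion of men with a complication, a confidence interval, a limit on acceptable harm or a severity grading. Both carry the same title, which puts safety first: "Analysis of the Safety and Efficacy of Administering Umbilical Cord Mesenchymal Stem Cell Secretome".

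**The concern.** Hematoma, local bleeding and infection are possible consequences of an intracavernosal injection. In a single-group trial, the safety result is the proportion of treated men who had each event and the highest true rate the data allow. A before/after test asks a different question. If the men start without these events, every change is a worsening, and the test asks only whether the rate differs from zero. It estimates no rate and sets no limit.

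With few men, such a test is likely to be non-significant even when complications are common, and with no events it has nothing to work on. Either outcome could be read as reassurance while a high complication rate remains compatible with the data. The SAP states no such reading rule, but nothing in it requires the counts that would prevent the misreading.

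The SAP's reference to several unspecified times adds a smaller uncertainty. If it means a separate test at each visit, events could be split across visits and each test would see fewer of them. The documents do not say.

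Pain is a separate case. No scale is given; if pain is a rating, a paired Wilcoxon test is legitimate.

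**Working it through.** **No figure to reproduce.** The documents give no sample-size calculation, alpha, expected complication rate or harm limit.

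**Inputs**
- Number of men: 12 as base case. The Protocol (Materials and Methods) refers to a "pre-post-test research design with 12 subjects of severe ED non-responsive to sildenafil", but the preceding sentence describes an earlier study "which used stem cell injections in erectile dysfunction patients", so it is not certain which study the 12 belongs to. Range used: 10 to 20.
- Assumed, not in the documents: events absent before injection; alpha 0.05; exact two-sided signed-rank test.

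**Step 1: the p-value.** Let k men have the event. All k non-zero differences point the same way, so only one of the 2^k sign patterns is as extreme in that direction:

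p = 2 × 0.5^k

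The number treated, n, does not appear. Full enumeration of sign patterns gives the same values for graded scores (1, 2, 3, 1, 2 gives 0.0625; 3, 1, 2, 2, 1, 3 gives 0.03125), so grading does not change this.

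| Men with event (k) | 1 | 2 | 3 | 4 | 5 | 6 |
|---|---|---|---|---|---|---|
| Exact two-sided p | 1.00 | 0.50 | 0.25 | 0.125 | 0.0625 | 0.031 |

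The first significant count is 6.

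**Step 2: the rates behind one p-value.** The intervals are Clopper-Pearson, with lower limit the 0.025 quantile of Beta(k, n−k+1) and upper limit the 0.975 quantile of Beta(k+1, n−k).

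| | n = 10 | n = 12 | n = 20 |
|---|---|---|---|
| p with 5 events | 0.0625 | 0.0625 | 0.0625 |
| Rate with 5 events | 50% | 42% | 25% |
| Exact 95% CI | 18.7–81.3% | 15.2–72.3% | 8.7–49.1% |
| Rate at 6 events | 60% | 50% | 30% |
| Chance of 6 or more events, true rate 30% | 4.7% | 11.8% | 58.4% |

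The last row is the binomial tail P(X ≥ 6 | n, 0.3).

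**Step 3: no events.** Every difference is zero, so there are no ranks. The upper end of the exact two-sided 95% interval is 1 − 0.025^(1/n); the one-sided 95% limit is 1 − 0.05^(1/n).

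| | n = 10 | n = 12 | n = 20 |
|---|---|---|---|
| Upper end, two-sided 95% CI | 30.8% | 26.5% | 16.8% |
| One-sided 95% upper limit | 25.9% | 22.1% | 13.9% |

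**Step 4: other forms of the test.** The SAP names no variant, so these are equally possible.

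| Form | First significant count | p at that count | Chance of reaching it, n = 12, true rate 30% |
|---|---|---|---|
| Exact, two-sided | 6 | 0.031 | 12% |
| Exact, one-sided | 5 | 0.031 | 28% |
| Normal approximation, continuity-corrected | 5 | 0.037 | 28% |
| Normal approximation, uncorrected | 4 | 0.046 | 51% |

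At n = 20, the chance rises to 76% for a threshold of 5 and 89% for a threshold of 4. The threshold moves, but no row yields a rate or a limit.

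**The case against.** The strongest reply is that the figures depend on choices the SAP leaves open. Five events miss significance only in the exact two-sided form; the one-sided exact test and both normal approximations would call them significant. Coding, baseline status, alpha and the number of men are also assumed. This stands for the size of the problem, which is why the working shows a threshold of 4 to 6 events. It does not touch the structural point, because no variant produces an incidence or a bound.

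Second, the zero-event limit depends on the interval: 26.5% is the upper end of a two-sided 95% interval for 12 men, and the one-sided 95% limit is 22.1%. Both are valid and must be labelled. Some software also returns p = 1 rather than an error when all differences are zero. That value carries no information about the rate, so the practical conclusion is the same.

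Third, the SAP is skeletal throughout. It names a test for each outcome and plans no descriptive statistics for any, so counts are not excluded and may well be reported. That is fair, and it is wrong to say that the trial will report no complication rate. But safety leads the title, and the only pre-specified result for these outcomes is a p-value for change, which cannot stand in for an incidence.

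Finally, misreading a null result as safety is a risk, not something the SAP proposes. This also stands.

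**Conclusion.** The concern holds. For hematoma, local bleeding and infection, the plan as written delivers a p-value for change but no complication rate and no upper limit on harm, and neither document plans another safety analysis. Confidence in that is high, since it follows from the complete text of two short documents.

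The size is conditional on events being absent before injection and on alpha 0.05. With the exact two-sided test and 12 men, half must have a complication before the test is significant, and at a true rate of 30% the chance of that is about 12%. With no events, rates up to 26.5% (two-sided 95% interval) or 22.1% (one-sided 95% limit) remain compatible with the data. Other forms of the test lower the threshold to 4 or 5 men, and a different trial size changes the figures as shown; the conclusion is the same throughout.

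This should be fixed. The trial remains feasible, but its first-named objective has no planned estimate.

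**What to change.** In section 1 of the SAP, for hematoma, local bleeding and infection (and for pain if it is recorded yes/no):

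- Replace the Wilcoxon test with the number and percentage of treated men with the event at any recorded time after injection, each with an exact Clopper-Pearson 95% confidence interval. Add a line for men with any of these complications.
- If an event is graded, count any grade and also tabulate the worst grade per man.
- State the zero-event upper limit for the number of men actually treated and say which limit it is (for 12 men, 26.5% as the upper end of a two-sided 95% interval).
- State that p > 0.05 will not be taken as evidence of safety.
- If events are recorded only at visits, describe the measure as events observed at visits.
- If pain is a rating, the paired Wilcoxon test may stay, with the post-injection incidence of pain reported beside it.

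**Cost.** This is a wording change if events are already recorded after injection, and it needs no additional men. Neither document gives a visit schedule or a method of capturing events, so counting events between visits could need a change to data collection. If that is no longer possible, the measure is limited to what was seen at visits. The downside is a less favourable safety statement, because the intervals in a trial this small are wide.

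### SAP 1 plans only a paired before/after test for hematoma, local bleeding and infection, so it yields no any-time event count and can understate harm

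*SAP*

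**What the plan says.** The protocol, under Materials and Methods, describes the design in one line: "This study is an experimental study with a pre-post-test design". On safety it says: "The safety parameters measured included pain, hematoma, local bleeding, and infection". It gives no method of ascertainment, recall window or timing for these items.

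SAP 1 is the only other text on them. It puts them in one list with the efficacy questionnaires, "outcomes such as pain, hematoma, local bleeding, infection, and changes in IIEF-5, EHS, and morning erections", and gives a single instruction for the whole list: "The Wilcoxon analysis will be used to compare outcomes before and after intervention at various times". SAP 2 uses the same phrase, "compare outcomes before and after intervention at various times", for SPL, FPL and circumference.

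The only follow-up time fixed anywhere is in SAP 3, for the Doppler measurements of PSV and artery diameter: "before and 1 month after the intracavernosal injection intervention".

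**The concern.** A questionnaire score exists at every moment, so comparing its value before and after treatment is a sensible summary. A hematoma, a bleed or an infection is different: it starts, may resolve, and does not exist as a treatment complication before the injection. What a reader wants to know is how many of the men injected had one at any time. A paired comparison at separate times does not give that number.

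Two losses can follow. A man with no after value contributes no pair, and if he left because of a complication, that complication leaves the comparison with him. If the value at each time is status on the day, an event that has already resolved is read as absent. Each loss lowers the number of men counted as having had an event. Safety is in the trial's title, and with about 12 men each uncounted man moves the result by 1/12, about 8 percentage points. Replacing the Wilcoxon test with a proportion at the analysis stage would not recover events that were never recorded, so the definition of the event has to change as well as the summary.

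**Working it through.** The documents give no event rate, power, alpha or dropout, so there is no figure of the plan's own to reproduce. The calculations below show the direction and possible size.

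**1. What is specified**

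| Item | Protocol | SAP |
|---|---|---|
| Which events | Listed | Listed with the questionnaires |
| How events are captured | Not stated | Not stated |
| Safety assessment times | Not stated | Several, unspecified |
| Summary | Not stated | Paired Wilcoxon only |
| Count of men with any event since injection | Not stated | Not stated |
| Men without a later assessment | Not stated | Not stated |

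**2. Inputs**

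- n = 12, from Materials and Methods: "pre-post-test research design with 12 subjects of severe ED non-responsive to sildenafil". The sentence follows one about a cited earlier study, so it is an assumption that 12 is this trial's size.
- p, the share of men who have a given event at any time: assumed 10%, 20% or 30%.
- d, the share of those events still visible when status is read: assumed 1, 0.5 or 0.25. Counting any occurrence corresponds to d = 1, taking recall as complete.

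**3. Chance that at least one event is recorded**

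Formula: 1 − (1 − p·d)^12.

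For p = 20%:

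- d = 1: 1 − 0.80^12 = 93%
- d = 0.5: 1 − 0.90^12 = 72%
- d = 0.25: 1 − 0.95^12 = 46%

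| p | Any occurrence (d = 1) | d = 0.5 | d = 0.25 |
|---|---|---|---|
| 10% | 72% | 46% | 26% |
| 20% | 93% | 72% | 46% |
| 30% | 99% | 86% | 61% |

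**4. A man who leaves before his event is recorded**

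Suppose 2 of 12 men have an event and one of them leaves first.

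- True proportion: 2/12 = 16.7%.
- Dropped from the pairs: 1/11 = 9.1%.
- Kept in the denominator as event-free: 1/12 = 8.3%.

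Both treatments understate the rate. The first is what a paired test does by default; the documents do not state either. Losing a man who had no event would instead raise the complete-case proportion (2/11 = 18.2%). The one-way direction therefore applies to the count of events, and to the proportion when departure is linked to a complication.

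**5. What the paired test can show**

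With no events at baseline and k men affected at one time, all non-zero differences are equal and in one direction. The exact two-sided p-value is 2 × 0.5^k: 0.0625 for k = 5 and 0.031 for k = 6. So at least 6 men must have the event at the same time point for p < 0.05. If p = 30%, the binomial chance of 6 or more among 12 is 11.8% with d = 1, and 0.5% with d = 0.5. The SAP does not name the exact version. A tie-corrected normal approximation without continuity correction gives z = √k, so k = 4 (z = 2.0) would pass, but that approximation is weak with so few pairs. On either version, a non-significant result says little about safety.

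**6. What an exact interval shows**

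Exact two-sided 95% intervals: 0/12 gives 0% to 26.5% (upper limit 1 − 0.025^(1/12)); 1/12 gives 0.2% to 38.5%; 3/12 gives 5.5% to 57.2%. Even a correct count of zero leaves a true rate of about a quarter within the interval, which a paired p-value does not show.

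**The case against.** The strongest reply is that the SAP sentence describes an analysis, not data collection. A site could record any hematoma since the injection at each assessment and still follow the SAP. This stands. A reader might infer that the plan collects events as status on the visit day, records transient events as absent, and so builds in an under-count that every later summary inherits. The documents do not say so. The status reading has support: the paired test needs a before value, which for an event since injection could only be a trivial zero; the same sentence governs IIEF-5 and EHS; and SAP 2 uses the same phrase for point measurements. That makes it the more natural reading, but still an inference.

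Three further replies also stand:

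- A man who leaves early would normally be missing from a paired test, not coded as event-free, and no withdrawal rule says otherwise.
- A reader might take 1 month as the first safety check. That time belongs only to PSV and artery diameter, and earlier safety readings, which would reduce the loss, are equally compatible with the text.
- How long these events last, and whether any man will leave, is not in the documents. That is why d is an assumption shown over a range.

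None of this supplies what is missing. Even if events are captured cumulatively, the only planned summary is a paired test that reports no incidence and needs an after value.

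**Conclusion.** The concern holds as a gap in the plan, not as a demonstrated under-count. As written, SAP 1 gives no cumulative incidence for hematoma, local bleeding or infection, and its paired comparison leaves out any man without an after value. Events that resolve between assessments are also missed if the values are status readings, which is likely on the wording but not stated. Uncounted events can only make the treatment look safer.

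The size of the loss cannot be determined, because capture, safety times and withdrawals are unspecified. For a 20% event rate in 12 men, the chance of recording at least one event ranges from 93% (any occurrence counted) to 46% (a quarter still visible). These figures rest on the assumed p and d, and on 12 being this trial's size; another n changes the figures but not the direction. The documents do not support saying that the trial's safety conclusion will be too favourable, only that the plan does not prevent it. The change is worth making because it is cheap and the possible error favours a finding of no harm.

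**What to change.** In SAP 1, take hematoma, local bleeding and infection out of the before/after comparison and specify the following:

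- **Definition:** any occurrence since the injection. At each planned assessment, ask about the whole interval since the injection or last contact, and record onset and resolution dates where obtainable.
- **Summary:** for each event, the number and proportion of men with at least one occurrence, with an exact 95% interval, among all men injected, including those without a later assessment. State how many had no later contact, so that they are not taken as event-free. In the withdrawal example in the working, that would show 1/12 recorded with one man unknown, so between 8.3% and 16.7%.
- **Pain:** keep the scores at each time and add the worst pain since injection.
- **Timing:** state the times at which safety is assessed.

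The cost is SAP and case report form wording, plus one question at assessments already planned. The drawbacks are that events between assessments rest partly on patient recall, and that dates may be incomplete if data collection has already begun. The documents mix past and future tense and do not settle that point.

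### Does SAP section 3 need a rule for how the right and left cavernosal arteries enter the paired t-test, and a named test for lumen diameter?

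*SAP*

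**What the plan says.** SAP section 3 covers two Doppler measurements taken in the flaccid state, which it calls "both research parameters, namely Peak Systolic Velocity (PSV) and the diameter of the proximal side cavernosum artery lumen". Both are recorded before the injection and 1 month after it. The section's only analysis sentence is: "The difference in PSV of the right and left cavernosum arteries will be analyzed using the Paired T-test".

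SAP sections 1 and 2 assign tests to other outcomes and do not list diameter. The Protocol (Materials and Methods) describes a pre-post study "with 12 subjects of severe ED non-responsive to sildenafil". It places Doppler examinations among the efficacy parameters and mentions arterial insufficiency predicted "using a PSV cutoff value of 10cm/s in the cavernosal arteries". Neither document says how the two sides are combined, which outcome is primary, or what significance level applies.

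**The concern.** Each patient contributes two arteries, and the analysis sentence does not name the unit of analysis. Taken strictly, it allows three before-after analyses:

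- a separate test for each side;
- one test on the within-patient average;
- one test on all arteries together, 12 × 2 = 24 pairs.

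The third treats two vessels of one man as independent. It would overstate precision and raise the false-positive rate. The first two are both valid but can lead to different conclusions, so an unwritten rule leaves room to choose after seeing the results. The wording "The study subjects underwent PCDU examination while flaccid" is in the past tense, which adds to that worry.

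Diameter also seems to be left without a test. It is one of the section's two parameters, yet the analysis sentence mentions PSV only, and no right or left side is given for it. At stake would be the credibility of the Doppler results.

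**Working it through.** **No figure to reproduce.** The documents give no sample-size calculation, alpha, effect size, SD or right-left correlation. The only numerical input is 12 patients. The sentence with that number directly follows a reference to an earlier study, but its population matches this trial's title, so 12 is read as this trial's size. Everything else below is assumed: normally distributed changes, two-sided alpha 0.05, equal SDs on the two sides unless stated, and right-left correlation of changes ρ.

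**1. What pooling would do.** The variance of the mean of 24 arteries is SD² × (1+ρ)/24, so the effective number of independent units is 24/(1+ρ): 24/1.0 = 24 at ρ = 0, 24/1.5 = 16 at ρ = 0.5, and 24/2.0 = 12 at ρ = 1. A pooled t-test acts as if the number were always 24. Its 95% CI half-width is about t(23)/√24 = 0.422 SD, against t(11)/√12 = 0.635 SD for one side with 12 pairs. Simulated with 400,000 trials per scenario and no true change:

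| ρ | 0.1 | 0.3 | 0.5 | 0.7 | 0.9 |
|---|---|---|---|---|---|
| False-positive rate, 24 pooled | 6.1% | 8.5% | 11.2% | 13.7% | 16.8% |

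The test on the within-patient mean stays at about 5% at every ρ examined. Pooling would therefore matter if it were planned.

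**2. Is pooling planned?** Set the parts of section 3 side by side. The subjects are measured at two times, each artery is named, and the test is a paired t-test. Together these give a before-after pair within each patient, once for the right artery and once for the left. Nothing refers to combining arteries, and the number 24 does not appear. The rates in step 1 describe a misuse of the named test, not the plan.

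**3. How much do the sound options differ?** Suppose the true change is 0.7 SD on both sides. Counting right, left and mean as three analyses, they do not all agree in 52%, 44%, 36%, 27% and 15% of trials for ρ = 0.1 to 0.9. That count overstates the effect of the missing rule, because right and left together form one option. When they split, the per-artery analysis shows the split. At ρ = 0.5 the disagreement divides as follows:

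- total: 36.2 percentage points;
- right differs from left: 33.8 points;
- right and left agree but the mean differs: 36.2 − 33.8 = 2.4 (2.3 before rounding).

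At ρ = 0.9, 15.1 of 15.2 points are right differing from left. The size also depends on the assumed effect. With equal SDs, total disagreement falls to 8–21% at 1.0 SD, 1.5–3.3% at 1.3 SD and about 0.2% at 1.6 SD. With side SDs in the ratio 1.5 it falls more slowly: 33–47% at 1.0 and 20–23% at 1.3 of the smaller SD.

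**4. Would fixing one option improve the analysis?** At ρ = 0.5 and a change of 0.7 SD on both sides, power is 72% for the mean and 64% for either side with Bonferroni. If only one side changes, it is 25% for the mean and about 48% for Bonferroni. Neither is better throughout, and the documents give no SDs or correlation on which to choose.

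**5. Diameter.** The section heading covers PSV and diameter, the text introduces them as a pair of parameters, and both share the same two time points. Diameter is a continuous before-after measurement like PSV, so the paired t-test is the evident choice. The word proximal gives the position along the vessel, and the side or sides analysed are simply those measured.

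**The case for a change.** The strongest case for a change is that the natural reading is still only a reading. The text could even be taken as a right-versus-left comparison, although the two time points make that unlikely. Nothing expressly rules out pooling.

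Under the per-artery reading, the plan does not say how a result on one side only is to be interpreted. With no true change, at least one side reaches p<0.05 in 9.7% of trials at ρ = 0, 9.2% at 0.5 and 7.9% at 0.8. Where the sides split, an analyst who had averaged would report a single verdict instead of a mixed one, so the choice is not wholly without effect. A few sentences would settle all this at almost no cost.

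These observations are correct as far as they go. But failing to exclude a misuse is not the same as planning it. A one-sided result is visible to any reader when both sides are reported, as the naming of both arteries leads one to expect. The either-side rates are measured against a 5% level that the plan never sets, in a single-group study with no primary outcome and no confirmatory claim attached to PSV. The past tense is weak evidence that data had been seen, since the same section puts the analysis in the future tense and the Protocol mixes tenses when describing the design. What stands is that the wording could be fuller.

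**Conclusion.** No change to the plan follows. Section 3 is most naturally a pair of before-after paired t-tests, right and left, with one pair per patient, and the same test for diameter on whichever side or sides were measured. That analysis is valid.

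The 6% to 17% false-positive rates apply only to a 24-artery analysis that the plan does not propose. They rest on assumed correlations of 0.1 to 0.9 and an assumed 5% level. Disagreement caused by the unwritten choice itself, where both sides agree and the mean does not, is about 2 percentage points in the illustrative case (0.7 SD change, ρ = 0.5, equal SDs). The rest is a right-left split, which per-artery reporting shows.

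What remains is missing detail: the unit of analysis, the reading of a one-sided result, and the test and side for diameter. Spelling these out would be a courtesy to the reader. It would not replace a weaker method with a better one, and the effect is confined to the Doppler outcomes.
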